### **8.1.2. Procedures in the Event of (Suspected) COVID-19**

#### **8.1.2.1. Passive Follow-up (As of Amendment 7)**

As of Amendment 7, active follow-up of suspected COVID-19 episodes will be replaced by a passive follow-up approach. For COVID-19 events that are ongoing at the time of informed consent:

[figure not shown]
- a. Participant will be instructed to stop using the eCOA.
- b. Any outstanding activities planned for the follow-up of COVID-19 events will end as of the consent.
- c. No further sampling for participants and no Day 1-2, Day 3-4, and Day 29 visit will be performed
- d. MRU and MA-COV forms are no longer to be completed

The eCOA will be stopped based on approval of protocol Amendment 7 at each study site. From that point onwards, active participants are no longer able to use eCOA.

For new suspected COVID-19 episodes no samples will be collected in the context of the study. Site staff will collect information on new COVID-19 episodes at scheduled time points and report these as SAEs, AEs, or MAAEs, as applicable. Participants may contact the site at any time in between scheduled visits to report COVID-19 episodes. Concomitant medications for each COVID-19 episode are to be reported into the eCRF as well as any laboratory confirmation of COVID-19, if available.

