### 8.1.3. Efficacy Assessments

Up to Amendment 7, identification and molecular confirmation of SARS-CoV-2 infection and symptomatic COVID-19 will be performed throughout the study as described in Section 8.1.2.2. Up to Amendment 7, the ePRO to evaluate VE parameters will be the SIC. See Section 8.1.3.1 for Case Definition of Moderate to Severe/Critical COVID-19 and Section 8.1.3.2 for Case Definition of Mild COVID-19. As of Amendment 7, no identification or molecular confirmation of SARS-CoV-2 infection and symptomatic COVID-19 will be done.

Molecular confirmation of SARS-CoV-2 infection by a central laboratory will be used for the analysis of the case definition.

All COVID-19 cases will be assessed independently by a Clinical Severity Adjudication Committee (see Section 8.1.3.6). Classification of severity will be based on the highest degree of severity during the observation period (see Sections 8.1.3.1 and 8.1.3.2).

As several of the prespecified criteria for suspected COVID-19 overlap with vaccine-related reactogenicity, investigators' clinical judgement is required to exclude vaccine-related events when assessing suspected COVID-19.

The occurrence of COVID-19-related hospitalization and COVID-19-related complications (such as but not limited to hyperinflammatory syndrome, pneumonia, neurological or vascular complications, severe pneumonia, severe neurological or vascular events, acute respiratory distress syndrome, renal complications, sepsis, septic shock, death) will be monitored throughout the study (up to protocol amendment 7).

As a secondary objective, VE in the prevention of asymptomatic SARS-CoV-2 infection and mild COVID-19 will be analyzed. For samples collected prior to implementation of Amendment 7: an immunologic test for SARS-CoV-2 seroconversion (ELISA and/or SARS-CoV-2 immunoglobulin assay) based on SARS-CoV-2 N protein, may be performed to identify cases of asymptomatic

infection. This assay will be performed on samples obtained (if prior to Amendment 7) at Day 1 (pre-vaccination), Day 71, Month 6/Unblinding Visit, and Month 18.

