#### **8.1.3.5. SARS-CoV-2 Seroconversion Assessment**

An immunologic test for SARS-CoV-2 seroconversion (ELISA and/or SARS-CoV-2 immunoglobulin assay) based on SARS-CoV-2 N protein may be performed to identify cases of asymptomatic infection on samples obtained at Day 1 (pre-vaccination), Day 29, Day 71, Month 6/Unblinding Visit, Year 1 + 28 days for participants who received booster vaccination, Year 1 + 72 days for participants who received booster vaccination, and Month 18 (24 weeks after Year 1 Visit). (see Section 8.1.4).

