**Table 4: Sample Size and Distribution of the Homologous Booster Subset Age Groups**

Study Vaccine	Subgroup 1a	Subgroup 1b	Subgroup 2a	Subgroup 2b
$5 \times 10^{10}$ vp	50	50	50	50
vp = virus particles				
Subgroup 1a: healthy $\geq 18$ to $< 60$ year old adults without relevant comorbidities .				
Subgroup 1b: $\geq 18$ to $< 60$ year old adults with relevant comorbidities .				
Subgroup 2a: healthy $\geq 60$ year old adults without relevant comorbidities .				
Subgroup 2b: $\geq 60$ year old adults with relevant comorbidities .				

**Heterologous Booster Subset:** The Heterologous Booster Subset will include approximately 400 participants, as described in [Table 5](#). This subset will include participants in the study who received placebo in the double-blind phase and have received primary vaccination with an mRNA vaccine or another authorized COVID-19 vaccine including protein, inactivated, and adenovector based vaccines outside the study, who subsequently remained in the study and subsequently received an Ad26.COV2.S booster vaccination in the study. Participants who already received an additional COVID-19 vaccination after the primary regimen outside the study will not be included in the Heterologous Booster Subset. Participants will be selected out of countries where these vaccines were authorized for emergency use or are licensed. Participants in the Heterologous Booster Subset will have blood collected pre booster vaccination, and 28 days, 72 days, 6 months, and 1 year post booster vaccination for humoral immunogenicity assessment (see Section [1.3](#)).

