### 9.3. Populations for Analysis Sets

For purposes of analysis, the following populations are defined:

**Full Analysis Set (FAS):** All randomized participants with a documented study vaccine administration, regardless of the occurrence of protocol deviations and serostatus at enrollment. Analyses of safety will be performed on the FAS. Vaccine efficacy analyses can be repeated using the FAS.

**Safety Subset:** subset of the FAS for the analysis of solicited and unsolicited AEs.

**Per-protocol Efficacy (PP) population:** Participants in the FAS who receive double-blind study vaccine and who are seronegative at the time of double-blind vaccination and who have no other major protocol deviations that were judged to possibly impact the efficacy of the vaccine. Participants who became aware of their study vaccine allocation will cease to be part of the PP population. The PA of VE will be based on the PP population. The PP will be the main analysis population for efficacy analyses.

**Per-protocol Immunogenicity (PPI) population:** All randomized and vaccinated participants, including those who are part of the Immunogenicity Subset and for whom immunogenicity data are available, excluding participants with major protocol deviations expected to impact the immunogenicity outcomes. In addition, for participants who experience a SARS-CoV-2 event (molecularly confirmed), samples taken after the event and samples taken outside protocol windows will not be taken into account in the assessment of the immunogenicity. The PPI population is the primary immunogenicity population. For key tables, sensitivity immunogenicity analyses will also be performed on the FAS, including participants who are part of the Immunogenicity Subset for whom immunogenicity measures are available. Excluded samples might be taken into account as well in the sensitivity analysis. Analyses of vaccine immunogenicity and immune correlates of risk will be based on PPI.

The populations for the open-label cross-over, booster and passive follow-up phase are described in the SAP.

The list of major protocol deviations to be excluded from the efficacy for the double-blind analysis and/or immunogenicity analyses will be specified in the SAP and/or this list will be reported into the protocol deviation dataset of the clinical database before database lock and unblinding.

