If an efficacy signal is triggered before the required 8-week follow-up after double-blind vaccination of 50% of participants is reached, an additional analysis will be performed when that follow-up timepoint is reached. If the time between the efficacy signal and the required 8-week median follow-up is too short to make a difference in terms of preparing two analyses, then a single analysis will take place at the time of the 8-week median follow-up. The analysis at the time of the 8-week median follow-up is considered the primary analysis.

If more than 154 primary endpoints are observed for events with onset at least 28 days after double-blind vaccination before the 3 conditions above are met, a single analysis will take place as soon as the conditions are met, using the full 2.5% one-sided significance level.

If the prespecified boundaries and above conditions are met, the SSG will inform the DSMB and, if deemed appropriate by the DSMB, a meeting with the DSMB and the Oversight Group will be set up to discuss the efficacy signal. Upon this meeting the sponsor representative on the Oversight Group can trigger internal decision procedures to initiate health authority interactions based on the

outcome of the study. However, the study sites and participants will remain blinded to allow for evaluation of durability of VE. Sponsor personnel will be unblinded at the time of the primary analysis. If an efficacy signal is triggered before the required 8-week follow-up after double-blind vaccination of 50% of participants is reached (defined as “snapshot analysis”), selected sponsor personnel will be unblinded at the time of the snapshot analysis.

A positive RT-PCR or other molecular diagnostic test result obtained from a central laboratory will be utilized to define a molecularly confirmed case of COVID-19. Sensitivity analysis comparing cases also including a positive RT-PCR test result from any source, including external to the study, will be performed for each diagnostic category individually (mild, moderate, severe, moderate+severe, and medical utilization [hospitalization, ICU care, mechanical ventilation, ECMO]).

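### The per-protocol immunogenicity rule drops samples only after molecularly confirmed infection, so N-only seroconverters keep post-infection titres, and the protocol conflicts on whether N-serology continues after Amendment 7

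*Protocol*

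**What the plan says.** **Exclusion rule.** Protocol Section 9.3 makes the PPI set the primary immunogenicity population. Its sample-level exclusion has two triggers. The first is infection: "for participants who experience a SARS-CoV-2 event (molecularly confirmed), samples taken after the event" are left out. The second is sampling outside the protocol windows. N-serology is not one of them.

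**What counts as infection elsewhere.** Section 8.1.3.4 classes a participant who turns N-seropositive without qualifying symptoms as an asymptomatic or undetected case. Section 9.5.2 includes such cases in vaccine efficacy against any infection.

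**What counts as molecular confirmation.** Section 9.5.1 says that a positive result "obtained from a central laboratory will be utilized to define a molecularly confirmed case of COVID-19".

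**Amendment 7.** Section 8.1.3 states: "As of Amendment 7, no identification or molecular confirmation of SARS-CoV-2 infection and symptomatic COVID-19 will be done". Section 8.1.2.1 adds: "For new suspected COVID-19 episodes no samples will be collected in the context of the study". Outside laboratory results are still recorded when available (Sections 8.1.2.1 and 8.3.1).

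**Sampling that continues.** Section 8.1.4 keeps humoral sampling in the Immunogenicity Subset (about 400) at Month 18 and Year 2. The booster subsets (about 200 homologous and 400 heterologous) are sampled before the booster and "28 days, 72 days, 6 months, and 1 year post booster vaccination for humoral immunogenicity assessment".

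**N-serology.** Section 8.1.3 restricts it: "This assay will be performed on samples obtained (if prior to Amendment 7) at Day 1 (pre-vaccination), Day 71" and at later listed visits. Section 8.1.3.5 allows it at further visits, "and Month 18 (24 weeks after Year 1 Visit"), without an Amendment 7 limit.

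**The concern.** Immunogenicity samples are cleaned of infection so that a titre reflects the vaccine. That works only if the exclusion trigger matches the way the trial detects infection. Here the same participant can be infected for the efficacy analysis and clean for the immunogenicity analysis.

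The mismatch exists in the double-blind phase, whatever the SAP says about later phases. In the vaccine group it raises the geometric mean titre. In the placebo group it raises the comparator, so the bias in the vaccine-placebo contrast has no fixed direction.

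After Amendment 7 the concern is different. The study no longer produces the result that triggers the exclusion, and it is unclear whether it will still produce the serology that could replace it. Section 9.8.1 justifies about 600 booster-subset participants by the understanding they give of the magnitude and kinetics of the response to the booster. Unrecognised infections between booster and Year 2 would make that response look more durable than it is.

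**Working it through.** **1. Trigger against infection definition (double-blind phase).**

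| Infection detected by | Infection under 8.1.3.4 / 9.5.2 | Later samples dropped under 9.3 |
|---|---|---|
| Central-laboratory molecular test | Yes | Yes |
| N-seroconversion only | Yes | No |

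Section 8.1.3.5 lists N-serology at Day 1, Day 29, Day 71 and Month 6. These are the double-blind humoral visits in Section 8.1.4, so the second row can be closed with data the trial already foresees.

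**2. N-serology after Amendment 7.**

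| Place | Year 1 and booster +28/+72 days | Month 18 | Year 2 |
|---|---|---|---|
| 8.1.3 | Only visits before Amendment 7; these visits not listed | Only if before Amendment 7 | Not listed |
| 8.1.3.5 | +28/+72 days allowed; Year 1 itself not listed | Allowed, no limit | Not listed |
| 8.1.4 (serologic test for past or current infection) | Allowed | Allowed, no limit | Not listed |
| Appendix 2 (sero-confirmation row) | Not italic: continues | Italic: stops | Not listed |

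Appendix 2 says that italic text lapses with Amendment 7. Month 18 is therefore both allowed and stopped. Year 2 appears in none of the four places. The Schedules of Activities in Section 1.3 were not in the part of the protocol available here and would need checking too.

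**3. Possible size.** The plan gives no figure to reproduce, so this is illustration only. If a share p of a cell has had an unrecognised infection that multiplied the titre by F, the mean log titre rises by p·log F and the geometric mean is multiplied by F^p. Both p and F are assumptions.

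| F | p = 10% | p = 30% |
|---|---|---|
| 2 | 1.07 | 1.23 |
| 4 | 1.15 | 1.52 |
| 10 | 1.26 | 2.00 |

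For comparison, the 95% confidence factor of a geometric mean is 10^(1.96·SD/√n). With n = 50 per cell (Tables 4 and 5) and an assumed log10 SD of 0.4, 0.5 or 0.6, it is 1.29, 1.38 or 1.47.

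Inflation equals the middle value when p = log10(1.38)/log10(F), using 1.96 × 0.5/√50 = 0.1386 for the numerator:
- F = 2: 0.1386/0.3010 = 46%
- F = 4: 0.1386/0.6021 = 23%
- F = 10: 0.1386/1 = 14%

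Contamination can thus be negligible or can exceed sampling error.

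**4. Cost of exclusion.** At SD 0.5, dropping 10% of a cell (n = 45) changes the factor from 1.38 to 10^(0.98/√45) = 1.40. Dropping 30% (n = 35) gives 10^(0.98/√35) = 1.46.

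**The case against.** A reader might infer that Amendment 7 ends N-serology altogether and that late titres will therefore certainly mix vaccine and infection responses. The protocol does not support that reading:

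- **Scope.** The opening of Section 9 limits Sections 9.1 to 9.7 to the double-blind phase, and Section 9.3 leaves the cross-over, booster and passive follow-up populations to the SAP. It is not established that Month 18 and Year 2 samples fall under the 9.3 rule. Section 9.6 puts all immunogenicity analyses on the PPI set and Section 9.6.1 mentions cross-over recipients, but both lie inside the same scope limit.
- **N-serology.** Sections 8.1.3.5 and 8.1.4 still allow it at Month 18. Appendix 2 keeps it at Year 1 and 28 and 72 days after the booster. Table 6 lists N-protein antibody among the humoral assays without an Amendment 7 limit.
- **Other information.** Outside laboratory results are recorded. Section 9.3 does not itself name a central laboratory; that definition stands in the efficacy section. An outside positive test might therefore satisfy the wording.
- **Consequence.** Immunogenicity is descriptive, without formal testing, and the booster cohorts are not randomised.
- **Selection.** Dropping infected participants conditions on an event that may itself depend on titre, so the cleaned mean is not free of bias. Dropping samples on unverified self-report would make this worse.

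All of this stands against the stronger reading. It does not answer the double-blind mismatch, which rests on current text within the stated scope. Nor does it settle the N-serology conflict: an SAP can exclude only infections that were recorded, and participant report with occasional outside results will not find asymptomatic ones.

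**Conclusion.** The point holds in two parts of different strength.

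**Established:** the PPI rule retains post-infection titres of participants infected by N-seroconversion alone, although the protocol counts them as infected. The protocol also gives incompatible statements about N-serology at Month 18 after Amendment 7, and none of the sections examined lists it at Year 2.

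**A risk, not a certainty:** late subset titres may include unrecognised infection responses. Whether they do depends on open-label population rules in an SAP that is not at hand, on how the N-serology conflict is resolved, and on how complete outside test results are.

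The size is unknown. The range of 1.07-fold to 2.0-fold rests wholly on assumed infection shares of 10% to 30% and assumed titre rises of 2-fold to 10-fold. The low end lies well inside the sampling error of a cell of 50 and the high end lies outside it. The change should be made because it is cheap and the visits are already scheduled. No trial conclusion has been shown to be wrong.

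**What to change.** 1. In Section 9.3, extend the exclusion to samples from the first N-seroconversion onward, judged against the participant's own earlier sample. Carry the same rule into the open-label populations in the SAP.
2. Reconcile Sections 8.1.3, 8.1.3.5, 8.1.4 and Appendix 2 so that the N-antibody assay is run on the Month 18 and Year 2 subset sera already drawn. If primary vaccination with an inactivated vaccine can itself induce N antibody (an assumption; the protocol does not say), that subgroup needs a criterion based on a rise over its pre-booster sample.
3. Report geometric means with and without the excluded samples.
4. Use unconfirmed self-reported episodes only in a sensitivity analysis.

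**Cost.** No new visit or blood draw. At full retention and with no overlap, the assays would number (400 + 600) × 2 = 2,000. The Homologous Booster Subset is drawn from the Immunogenicity Subset and leaves that subset's schedule, so the true number is lower: 800 × 2 = 1,600 if all 200 came from it. Late cells lose some samples, with the modest loss of precision shown in the working.

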#### **9.4. Participant Information**

For all participants, descriptive statistics of demographic (eg, gender, age, height, weight, BMI, race, and other baseline characteristics) will be provided by vaccination group. Additional characteristics related to current work situation, living situation, and community interactions will be collected for risk factor analysis, if allowed per local regulations. Risk factor data initially collected from participants at screening prior to implementation of protocol Amendment 3 will also be used for the planned risk-factor analysis. See also Section [9.5.3](#).

#### **9.5. Efficacy Analyses**

The SAP will be finalized prior to first participant in and it will include a more technical and detailed description of the statistical analyses described in this section. This section is a summary of the planned statistical analyses of the most important endpoints including primary and key secondary endpoints.

##### **9.5.1. Primary Endpoints Evaluation**

The study is designed to test the co-primary hypotheses of VE in the PP population. For both co-primary endpoints the following hypothesis will be tested:

H0: VE  $\leq 30\%$  versus H1: VE  $> 30\%$  and each hypothesis will be evaluated at a 2.5% one-sided significance level.

The co-primary endpoints will evaluate:

- the first occurrence of molecularly confirmed, moderate to severe/critical COVID-19 according to the case definition in Section 8.1.3.1, with onset at least 14 days after double-blind vaccination (Day 15) with Ad26.COV2.S versus placebo, in the PP population, including all events from both age groups, with and without comorbidities.
- the first occurrence of molecularly confirmed, moderate to severe/critical COVID-19 according to the case definition in Section 8.1.3.1, with onset at least 28 days after double-blind vaccination (Day 29) with Ad26.COV2.S versus placebo, in the PP population, including all events from both age groups, with and without comorbidities.

Participants included in the seronegative analysis set are those participants with a negative SARS-CoV-2 serology test result at (double-blind) baseline.

Considering the current COVID-19 pandemic, early detection of VE will be very important. The proposed current analysis setup is designed for continuous sequential analyses (see Section 9.5.1.1), where statistical hypothesis testing is conducted repeatedly on accumulating data, generating an earliest possible signal if and when the splits between the number of events in placebo recipients are much larger compared to the Ad26.COV2.S-vaccinated group for both co-primary endpoints and in such a way that they are unlikely to be due to chance alone using a truncated SPRT. A successful primary efficacy conclusion will require:

1. Establishing the hypothesis H1: VE  $> 30\%$  for each co-primary endpoint

AND

2. A favorable split vaccine:placebo for the subset of primary endpoints meeting the severe/critical COVID-19 case definition (expressed as a VE point estimate against severe/critical COVID-19 molecularly confirmed endpoints  $\geq 50\%$ ) and a minimum of 5 events in the placebo group. This requirement needs to be met for severe/critical events with onset at least 14 days after double-blind vaccination and for severe/critical events with onset at least 28 days after double-blind vaccination.

AND

3. A VE of at least 50% for each co-primary endpoint.

To evaluate the primary null hypotheses: H0: VE  $\leq 30\%$  versus H1: VE  $> 30\%$  for the co-primary endpoints, the truncated sequential probability ratio test will be used based on accumulating event data for each co-primary endpoint. This boundary is set up using the fully sequential design and is derived in such a way to have approximately 90% power to detect a VE 60% using a one-sided alpha 0.025 against H0:VE  $\leq 30\%$ . For the evaluation of the favorable ratio against the severe/critical COVID-19 endpoints a sequential boundary corresponding to a VE point estimate

$\geq 50\%$  and a minimum of 5 events in the placebo group will be prespecified. The specific boundaries will be detailed in the SAP.

The monitoring can start as soon as the following conditions are met:

1. A minimum of 6 COVID-19 cases for the  $\geq 60$  years age group with onset at least 28 days after double-blind vaccination
2. At least 42 cases meeting the primary endpoints definition of moderate to severe/critical COVID-19 with onset at least 28 days after double-blind vaccination
3. A subset of at least 5 cases meeting the primary endpoints definition of severe/critical COVID-19 with onset at least 28 days after double-blind vaccination

No interim evaluation will be done, until those conditions are fulfilled. Monitoring for efficacy will not start before the above conditions 1-3 are met and will occur at least once a week by the SSG of the DSMB until the prespecified boundaries have been crossed.

The efficacy analysis will be triggered by either:

1. a) An interim evaluation if all prespecified efficacy boundaries have been met OR if 154 cases meeting the primary endpoints definition of moderate to severe/critical COVID-19 are observed for events with onset at least 28 days after double-blind vaccination

AND

1. b) The above 3 conditions are met.

OR, alternatively,

2. If the prespecified non-efficacy boundary has been met (evaluating events with start 28 days after double-blind vaccination) or when the harm boundary has been crossed. The decision rules for harm and non-efficacy are detailed in Section 9.5.1.1.

If an efficacy signal is triggered before the required 8-week follow-up after double-blind vaccination of 50% of participants is reached, an additional analysis will be performed when that follow-up timepoint is reached. If the time between the efficacy signal and the required 8-week median follow-up is too short to make a difference in terms of preparing two analyses, then a single analysis will take place at the time of the 8-week median follow-up. The analysis at the time of the 8-week median follow-up is considered the primary analysis.

If more than 154 primary endpoints are observed for events with onset at least 28 days after double-blind vaccination before the 3 conditions above are met, a single analysis will take place as soon as the conditions are met, using the full 2.5% one-sided significance level.

If the prespecified boundaries and above conditions are met, the SSG will inform the DSMB and, if deemed appropriate by the DSMB, a meeting with the DSMB and the Oversight Group will be set up to discuss the efficacy signal. Upon this meeting the sponsor representative on the Oversight Group can trigger internal decision procedures to initiate health authority interactions based on the

outcome of the study. However, the study sites and participants will remain blinded to allow for evaluation of durability of VE. Sponsor personnel will be unblinded at the time of the primary analysis. If an efficacy signal is triggered before the required 8-week follow-up after double-blind vaccination of 50% of participants is reached (defined as “snapshot analysis”), selected sponsor personnel will be unblinded at the time of the snapshot analysis.

A positive RT-PCR or other molecular diagnostic test result obtained from a central laboratory will be utilized to define a molecularly confirmed case of COVID-19. Sensitivity analysis comparing cases also including a positive RT-PCR test result from any source, including external to the study, will be performed for each diagnostic category individually (mild, moderate, severe, moderate+severe, and medical utilization [hospitalization, ICU care, mechanical ventilation, ECMO]).

The primary efficacy analysis will pool data across populations (both age groups with and without comorbidities) to evaluate the primary and secondary objectives. In addition, these will be supplemented with a subgroup analysis for age group (18 to <60 years,  $\geq 60$  years) and comorbidities employing a descriptive summary including 95% confidence intervals to describe the VE in each subpopulation. Depending on the recruited study population, the  $\geq 60$  years subgroup may be further subcategorized ( $\geq 70$  years,  $\geq 80$  years).

In addition, to assess potential time-effects of VE, the Kaplan-Meier method will be used to plot the estimated cumulative incidence rates over time for the vaccine and placebo groups. This method will be used to estimate cumulative VE over time, defined as  $[(1 \text{ minus ratio (vaccine/placebo)} \text{ of cumulative incidence by time } t) \times 100\%]$ . Divergence of vaccine and placebo curves may be utilized to estimate onset of efficacy following immunization.

Furthermore, VE will be evaluated in seronegative participants, counting primary endpoints since onset after double-blind vaccination.

At the time of unblinding, one additional analysis will be performed to assess the VE of Ad26.COV2.S vaccination versus placebo repeating analyses on all primary and secondary endpoints for the blinded portion of the study.

For the statistical analysis, individual data will be included up to the Month 6/Unblinding Visit for the double blind, placebo-controlled period. For the analysis of the open-label phase for an individual subject, data as of the Month 6/Unblinding Visit will be included in the analysis. For the evaluation of the durability of vaccine efficacy, the analyses of the open label part of the study will employ methods as described in Follmann (2020). Details will be provided in the SAP.

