## 9.2. Sample Size Determination

### 9.2.1. Efficacy (Total Sample Size)

The study TNE is determined using the following assumptions:

- a VE for molecularly confirmed, moderate to severe/critical SARS-CoV-2 infection of 60%.
- approximately 90% power to reject a null hypothesis of  $H_0: VE \leq 30\%$ .
- type 1 error rate  $\alpha = 2.5\%$  to evaluate VE of the vaccine regimen (employing the sequential probability ratio test [SPRT] to perform a fully sequential design analysis; detailed in Section 9.5.1).
- a randomization ratio of 1:1 for active versus placebo

Events are defined as first occurrence of molecularly confirmed, moderate to severe/critical COVID-19 according to the case definition in Section 8.1.3.1 in the PP population. The two co-primary endpoints will evaluate the events at least 14 days after double-blind vaccination (Day 15) and at least 28 days after double-blind vaccination (Day 29) with study vaccine.

Under the assumptions above, the TNE to compare the active vaccine versus placebo equals 154, based on events in the active vaccination and placebo group, according to the primary endpoints case definition of moderate to severe/critical COVID-19 (Section 8.1.3.1).

If the co-primary hypothesis testing is successful for both co-primary endpoints, secondary objectives will be evaluated against a null hypothesis employing a lower limit  $VE > 0\%$ . The

method to perform hypothesis testing of primary and secondary objectives preserving the FWER will be specified in the SAP. The FWER will be controlled at 2.5%.

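### The only VE-over-time summary named for the double-blind phase is cumulative VE, which can stay flat or even rise while current protection falls

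*Protocol*

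**What the plan says.** All of the text at issue is in Protocol Section 9.5.1 (Primary Endpoints Evaluation).

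- **Purpose of keeping the blind.** After an efficacy signal, "the study sites and participants will remain blinded to allow for evaluation of durability of VE".
- **Method for time effects.** The plan is, "to assess potential time-effects of VE, the Kaplan-Meier method will be used to plot the estimated cumulative incidence rates over time" for each arm. It continues: "This method will be used to estimate cumulative VE over time, defined as" 1 minus the ratio, vaccine to placebo, of cumulative incidence by time t, as a percentage. No interval-specific or hazard-based VE is named for the double-blind phase.
- **Time origin.** It is not stated. The same paragraph allows the separation of the two curves to be used to estimate when efficacy begins after the injection, which implies curves that start at vaccination.
- **Durability by name.** A cited crossover method is given for the open-label part only, with details left to the SAP. Double-blind data run to the Month 6/Unblinding Visit.

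**The concern.** Cumulative VE at time t averages all protection since time zero, weighted by placebo incidence. It does not estimate protection at time t. If counting starts at vaccination, two forces act on it as follow-up grows. The early weeks without protection become a smaller share of the average, which pushes it up. Waning pushes it down. The two can cancel, or the first can win.

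The placebo-controlled period up to Month 6 is the cleanest evidence on how protection changes with time, and durability is the reason given for prolonging it. If the VE summary named for time effects can show a level line during real waning, the report of that period may mislead on this question. The co-primary hypotheses do not use this summary and are not at stake.

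**Working it through.** **Check of the planning inputs.** Section 9.2.1 gives VE "a VE for molecularly confirmed, moderate to severe/critical SARS-CoV-2 infection of 60"%, "approximately 90% power to reject a null hypothesis of" VE ≤ 30%, one-sided 2.5% and "a randomization ratio of 1:1 for active versus placebo". In the conditional binomial of Section 9.5.1.1, π = (1 − VE)/(2 − VE), so π0 = 0.7/1.7 = 0.4118 and π* = 0.4/1.4 = 0.2857. The smallest total with exact α ≤ 0.025 and power ≥ 0.90 is T = 154 (reject if X2 ≤ 51; α = 0.0246, power = 0.908). The stated 154 events reproduce and are not in dispute.

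**Inputs for the time-effect check**
- From Section 9.2.1: annualized placebo incidence 1.4% in Months 1-3, 50% lower in Month 4 and 62% lower thereafter; about 20,000 per arm with 10% seropositive, so 20,000 × 0.9 = 18,000 per arm.
- Assumptions, not in the documents: VE is 0 to Day 14, rises linearly to 70% at Day 28, then changes linearly to a chosen value at Day 183. The protocol's calendar pattern is applied to time since vaccination, with months ending at Days 91 and 122.

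**Formula.** Cumulative VE(t) = 1 − [1 − exp(−Σ h(1 − VE))]/[1 − exp(−Σ h)], with h the daily placebo hazard. At this low incidence it is close to the weighted mean Σ h·VE/Σ h.

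**By hand, waning to 50%.** Relative incidence is 1, 0.5 and 0.38. The ramp on Days 15-28 contributes 14 × 0.375 = 5.25.
- Day 90: Days 29-90 contribute 62 × 0.6594 = 40.88. Then (5.25 + 40.88)/90 = 0.513.
- Day 183: Days 29-91 give 63 × 0.6587 = 41.50; Days 92-122 give 31 × 0.5 × 0.5981 = 9.27; Days 123-183 give 61 × 0.38 × 0.5387 = 12.49. Total weight is 91 + 15.5 + 23.18 = 129.68. Then (5.25 + 41.50 + 9.27 + 12.49)/129.68 = 0.528.

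The full formula gives 51.2% and 52.8%.

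**Results, protocol incidence, Day 90 to Day 183**

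| VE at Day 183 | Current VE | Cumulative VE from vaccination |
|---|---|---|
| 70% (no waning) | 70% to 70% | 54.0% to 58.9% |
| 50% | 62% to 50% | 51.2% to 52.8% |
| 30% | 54% to 30% | 48.4% to 46.7% |
| 0% | 42% to 0% | 44.2% to 37.5% |

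**Sensitivity to incidence.** With waning to 50%, cumulative VE rises under every pattern tried: 51.2% to 53.5% if incidence is constant, and 54.7% to 55.1% if it triples by Month 6. Waning to 30% gives 48.4% to 45.0% and 51.4% to 44.7% respectively.

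**Sensitivity to the origin.** Counted from Day 29 under protocol incidence, waning to 30% shows as 61.8% to 54.4%: a fall of 7.4 points against 24 in current VE. It is attenuated but visible.

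**The same data split by time since vaccination** (waning to 30%, 18,000 per arm, protocol incidence)

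| Days | Expected events, placebo/vaccine | VE |
|---|---|---|
| 29-56 | about 19/6 | 66% |
| 57-112 | about 31/14 | 56% |
| 113-183 | about 19/12 | 39% |

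In the last window the standard error of the log rate ratio is √(1/19.4 + 1/11.8) = 0.37, so an approximate 95% interval for VE is −25% to 70%.

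**The case against.** The strongest reply has five parts.

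- **The data are not at fault.** The plan also shows the arm-specific curves, and their late slopes carry current incidence in each arm. This stands. A reader might infer that the double-blind phase cannot show durability; that does not follow. Strong waning lowers even the cumulative figure, and period-specific VE can be computed from the same randomized data.
- **The protocol does not misread its own measure.** It labels the summary cumulative, defines it exactly, and nowhere says that a level line means no waning. This stands too. The criticism is that the measure fits its stated purpose poorly, not that a wrong interpretation is planned.
- **Durability is handled elsewhere, and detail belongs in the SAP.** The crossover method covers only the open-label part. Cut-points, stratification and tests can properly wait for the SAP. But Section 9.5.1 does not leave the measure open: it names and defines one.
- **The origin is inferred.** Correct. Counting from Day 29 weakens the effect, but waning is still attenuated.
- **Windows may be too imprecise.** At planning incidence, yes: the last-window interval above does not separate 39% from the early 66%. Section 9.2.1 reports incidence well above the planning value by Amendment 3, so those counts are cautious.

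A reader might also infer that cumulative VE always overstates late protection. It does not. Without waning it reads 58.9% at Day 183 against a true 70%. In a step example with constant incidence (VE 0% on Days 1-14, 66% on Days 15-84, 55% afterwards) it is 1 − (14 + 70 × 0.34)/84 = 55.0% at Day 84 and 1 − (14 + 23.8 + 84 × 0.45)/168 = 55.0% at Day 168. That level line hides an 11-point fall, yet at Day 168 it equals current VE.

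**Conclusion.** The point holds in a limited form. The only VE-over-time summary that the protocol names for the double-blind phase is cumulative and, counted from vaccination, a poor measure for the durability purpose the protocol gives. Under the protocol's incidence, a loss of 12 points in current VE between Days 90 and 183 appears as a gain of 1.6 points, and a loss of 24 points as a fall of 1.7. Complete loss by Day 183 does show, as a fall of 6.7 points.

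These sizes rest on assumed VE trajectories and an implied time origin. The incidence pattern, allocation and seroprevalence are the protocol's. Neither a claim that the double-blind phase cannot reveal waning nor a claim of bias in one fixed direction is supported. Section 3 and the SAP were not available for this review, so a better measure may be specified there. The co-primary tests are not affected.

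**What to change.** In Section 9.5.1, keep the Kaplan-Meier curves and cumulative VE as a descriptive display, including for onset, and state the time origin. Name as the time-effect measure for the double-blind phase either of these:

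- period-specific VE, 1 minus the incidence-rate or hazard ratio in the per-protocol population, in windows of time since vaccination starting at Day 15 or Day 29 and fixed before the final double-blind analysis; or
- a hazard ratio that varies with time since vaccination.

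Cut-points, stratification and any trend test can be set in the SAP. The cost is a wording change and a few extra model runs on data already collected. The downside is precision: late windows will have wide intervals, which should be reported and not smoothed over by returning to the cumulative figure.
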